7.3 Appropriateness of Measurements

All clinical assessments are standard measurements commonly used and generally recognized as reliable, accurate, and relevant in studies of cardiac and respiratory function.

8. SAFETY ASSESSMENTS

Safety will be assessed through monitoring of adverse events (AEs), physical examinations, laboratory tests, and electrocardiograms. Safety assessment frequency is shown in the Schedule of Assessments and Procedures.

8.1 General Safety Procedures

8.1.1 Vital Signs and Weight Measurements

Vital sign measurements, including systolic blood pressure (SBP), diastolic blood pressure (DBP), heart rate (HR)[beats per minute], respiratory rate (breaths per minute), and body temperature (in Celsius) will be obtained as clinically indicated. Weight (kg) will be obtained at the time of Screening and at End of Study. Height will be obtained at the time of Screening.

8.1.2 Physical Examination

Complete physical examination will include assessments of general appearance; skin and lymphatics; eyes, ears, nose, throat; cardiovascular system; respiratory system; abdomen/gastrointestinal system; urological system; musculoskeletal and neurological systems.

Other body systems may be examined. Clinically significant changes from Screening will be recorded as AEs.

8.1.3 Laboratory Measurements

Clinical laboratory measurements to be performed are listed below. The Schedule of Assessments and Procedures shows the time points at which blood will be collected for clinical laboratory tests and pregnancy testing. The Baseline for laboratory tests is the Screening assessment.

Category	Parameters
Hematology	Hemoglobin, hematocrit, RBC, WBC with differential (neutrophils, lymphocytes, monocytes, eosinophils, basophils), platelets
Chemistry	
Electrolytes	Sodium, potassium, chloride, bicarbonate, calcium
Liver function tests	AST, ALT, AP, total bilirubin
Renal function parameters	BUN, creatinine, eGFR calculation
Other	Glucose, albumin, total protein, uric acid, creatine kinase, serum pregnancy test

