4.3.1 Part I

Individual patient participation is expected to be approximately 5 weeks including:

- Screening: up to 30 days
- Intra-Operative: 3-8 hours
- Aerosolized Veletri Treatment administered in accordance with each site's standard of care guidelines (OR/ICU): 24+ hours (dependent on multiple factors)
- VentaProst Treatment (ICU): 24+ hours (dependent on multiple factors)
- End of Study: 4+ hours (dependent on multiple factors)

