8.1.4 Electrocardiograms

Twelve-lead electrocardiograms (ECGs) will be obtained at the visits designated on the Schedule of Assessments and Procedures. The Baseline for 12-lead ECGs is Screening.

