10.1.5 End of Study (ICU)

Once VentaProst dosing has been discontinued, the patient will undergo the following study-related procedures and evaluations within 24 hours of VentaProst discontinuation:

- Record all concomitant medications
- Record AEs
- Perform comprehensive physical examination
- Obtain vital signs and weight
- Perform 12-lead ECG
- Collect blood for clinical laboratory tests, including serum pregnancy test for women of childbearing potential

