12.7.2 Laboratory Values

Clinical laboratory results post-Baseline will be evaluated for markedly abnormal values. For the incidence of markedly abnormal laboratory values, each patient may be counted once in the laboratory parameter value high and in the laboratory parameter low categories as applicable.

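### Laboratory and ECG changes from a Screening baseline cannot be attributed to VentaProst, because bypass surgery intervenes and no pre-dose value is used

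*Combined protocol and SAP*

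**What the plan says.** **Baseline.** Section 8.1.3 of the protocol: "The Baseline for laboratory tests is the Screening assessment". Section 8.1.4: "The Baseline for 12-lead ECGs is Screening".

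**Timing.** Section 4.3.1 (Part I) gives "Screening: up to 30 days", then "Intra-Operative: 3-8 hours", then Veletri and VentaProst for 24 hours or more each. Section 4.3.2 (Part II) is the same without Veletri.

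**Schedule.** Tables 1 and 2 mark laboratory sampling and ECG at Screening and End of Study only. Sections 10.1.5 and 10.2.4 place the latter "evaluations within 24 hours of VentaProst discontinuation". The study is open-label (6.5), and neither part has a concurrent control.

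**Analysis.** Section 12.3 defines change as baseline against post-dose unless something else is specified. Section 12.7.2 adds: "Clinical laboratory results post-Baseline will be evaluated for markedly abnormal values". For ECG the plan gives only the frequencies and incidence rates of section 12.7.

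**Contrast within the plan.** Section 12.7.1 judges treatment-emergent adverse events against the pretreatment state. Hemodynamic parameters are measured before surgery and again before dosing (note 5 to Tables 1 and 2; section 10.1.4.1). Laboratory tests and ECG have no such pre-dose measurement.

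**The concern.** A safety change is informative about a drug when the reference value is taken shortly before the drug starts. Here the reference precedes a major operation that can itself move most of the panel, and nothing scheduled separates the operation from the drug.

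Three features of this trial make that matter:

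- No clinical trial of VentaProst has been done before (2.2.2). Safety is a secondary objective (3.2), and laboratory tests and ECGs are named in the key secondary safety endpoint (12.5.2).
- Section 2.2.5 names increased bleeding as a theoretical risk. Hemoglobin is the scheduled test closest to it, and surgery can change hemoglobin too.
- Exclusion criterion 12 removes patients with significantly abnormal laboratory values at Screening. Baselines are thus selected to be acceptable, and an abnormality caused by surgery will appear as new.

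Section 8.2.1 also allows expected post-operative events to go unrecorded as adverse events unless the investigator links them to the drug or device, or finds them unexpectedly severe or frequent. The laboratory and ECG summaries would be the natural check on that judgment. As planned, they cannot serve as one.

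**Working it through.** The plan states no calculation on this point, so there is no figure to reproduce.

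**Step 1. Length of the interval.** Inputs from sections 4.3.1, 4.3.2, 10.1.5 and 10.2.4: intra-operative 3 to 8 h; Veletri 24 h (Part I only) and VentaProst 24 h, both at their stated minimum; End of Study 4 to 24 h; Screening 0 to 30 days earlier (30 days = 720 h).

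| | Screening just before surgery | Screening 30 days before |
|---|---|---|
| Part I, short | 3+24+24+4 = 55 h | 775 h (32.3 days) |
| Part I, long | 8+24+24+24 = 80 h | 800 h (33.3 days) |
| Part II, short | 3+24+4 = 31 h | 751 h (31.3 days) |
| Part II, long | 8+24+24 = 56 h | 776 h (32.3 days) |

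The minimum VentaProst period is 24/80 to 24/55 = 30% to 44% of the interval in Part I and 24/56 to 24/31 = 43% to 77% in Part II when Screening is immediate. It is about 3% in both when Screening is 30 days earlier. These are shares of time, not of effect. They show only how much else the interval contains.

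**Step 2. Can the two time points separate the causes?** Let s be the chance that a patient is abnormal at End of Study from surgery and other background causes alone, and d the chance from VentaProst alone, taken as independent. Then

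P(abnormal) = 1 − (1 − s)(1 − d),

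and background causes alone would suffice in a share s/P of the abnormal patients. The documents give neither s nor d, so the values are assumptions.

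| s | d | P(abnormal) | s/P |
|---|---|---|---|
| 0.1 | 0.3 | 1 − 0.9 × 0.7 = 0.37 | 27% |
| 0.3 | 0.1 | 1 − 0.7 × 0.9 = 0.37 | 81% |
| 0.7 | 0.1 | 1 − 0.3 × 0.9 = 0.73 | 96% |
| 0.9 | 0.1 | 1 − 0.1 × 0.9 = 0.91 | 99% |

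The first two rows predict the same result with opposite explanations. Over s from 0.1 to 0.9 and d of 0.1 or 0.3, the share runs from 27% to 99%. Nothing measured under the plan narrows it.

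**Step 3. What the baseline label does.** The count in section 12.7.2 does not subtract a baseline. With a single scheduled End of Study result, renaming the baseline leaves the count unchanged. The label does affect change from Baseline under section 12.3. It would also affect section 12.7.2 if results from between surgery and dosing were captured, because they would then count as post-Baseline. The root cause is the missing post-operative, pre-VentaProst value together with the lack of a control.

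**Step 4. What about 10 patients per part can show.** Suppose s were known exactly and d = 0.3. An exact one-sided binomial test at 0.05 or less with n = 10 gives:

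| s | P(abnormal) | Reject at | Attained alpha | Power |
|---|---|---|---|---|
| 0.1 | 0.37 | 4 or more | 0.013 | 54% |
| 0.5 | 0.65 | 9 or more | 0.011 | 9% |
| 0.7 | 0.79 | 10 | 0.028 | 9% |

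A better reference value makes individual results readable. It does not make the study able to detect moderate effects.

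**The case against.** The strongest reply is that this is a small descriptive Phase 2a study that already has some protection. Laboratory and ECG abnormalities that cause symptoms, need intervention or change treatment become adverse events (8.2.5). Adverse events are judged against the pretreatment state (12.7.1), and all data are listed by patient (12.3). That stands for adverse-event reporting. It does not repair the laboratory and ECG summaries.

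A second reply is that a new baseline would not isolate the drug. In Part I the last value before VentaProst will normally have been drawn on Veletri, which is also epoprostenol. In Part II dosing may start in the operating room (4.5, 6.3.3.2), so no post-operative value may exist. That routine care yields the full panel and an ECG before dosing is an assumption. All of this stands, and it limits what the fix can claim.

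A reader might infer two stronger points that the documents do not support:

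- That the abnormalities measure the operation and not VentaProst. They reflect surgery, ICU care, Veletri in Part I and VentaProst together, and no rates are given to show which dominates.
- That a fall in platelet count due to the drug would be masked. Section 2.1 describes inhibited platelet aggregation, not a lower count, and the panel in section 8.1.3 has no aggregation test. The bleeding risk gives no basis for a numerical platelet effect.

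**Conclusion.** The concern holds as a limit on attribution. With a Screening baseline, one later scheduled assessment and no control, laboratory and ECG changes and post-Baseline laboratory abnormalities cannot be assigned to VentaProst as opposed to surgery, ICU care or, in Part I, Veletri. This conclusion rests on the schedule alone and needs no assumed rate.

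The size of the confounding cannot be estimated from the documents; the 27% to 99% range illustrates non-identifiability under assumed risks and independence. The post-Baseline wording applies to laboratory values, since no specific ECG analysis is given. The point does not affect the primary endpoint. It is a worthwhile, inexpensive improvement to the safety analysis.

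**What to change.** Set the following out in the SAP, which section 12.1 leaves open until database lock:

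- Keep Screening for eligibility and as one reference.
- Where the chart already holds a post-operative result from before the first VentaProst dose, abstract the last one per analyte and for ECG, and use it as the treatment baseline. Section 13.2.3 already recognises hospital charts, laboratory results and ECGs as source documents.
- Summarise change from this value beside change from Screening.
- Count a markedly abnormal value as treatment-emergent only if it was absent or less severe at the pre-dose value. This requires stated thresholds, which section 12.7.2 does not give.
- Do not pool the two baselines. Report how many patients have a pre-dose value for each analyte and for ECG, and show those without one against Screening only.
- State that the Part I pre-dose value is on Veletri and so isolates only the change after the switch, and that post-operative recovery remains a confounder in both parts.

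The cost is chart abstraction for about 20 patients (about 10 per part) and some added tables, with no new procedure. The downside is incomplete availability, especially for ECGs and for Part II patients dosed in the operating room.

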8.1.4 Electrocardiograms

Twelve-lead electrocardiograms (ECGs) will be obtained at the visits designated on the Schedule of Assessments and Procedures. The Baseline for 12-lead ECGs is Screening.

8.2 Adverse Events

8.2.1 Definitions

Adverse events are any untoward medical occurrence in a patient administered a pharmaceutical product and which does not necessarily have to have a causal relationship with this treatment. For the purposes of this study, this will include unanticipated medical events in the judgment of the investigator. Expected medical events are untoward clinical occurrences that are perceived by the investigator to occur with reasonable frequency in the day-to-day care of patients who have undergone cardiac surgery with CPB and who are treated in the ICU with mechanical ventilation. Such events will not be considered adverse events unless the investigator considers the event to be associated with study medication, study device, or to be unexpectedly severe or frequent for a patient.

A pre-existing condition or symptom is one that is present at the start of the study and is reported as part of the patient's medical history. A pre-existing condition or symptom should be reported as an AE only if its frequency, intensity or character worsens during study treatment.

All AEs that occur from the time of the first dose of study medication through the End of Study will be recorded and reported as Treatment-Emergent Adverse Events (TEAE). All AEs must be appropriately documented in the patient's medical chart and on the CRFs. When known, investigators should report syndromes rather than list symptoms associated with the syndrome.

All AEs that are ongoing at the conclusion of the study should be followed until: a) resolution/stable sequelae; b) the Investigator determines that it is no longer clinically significant; or, c) the study patient is lost to follow-up. If no follow-up is provided, the Investigator must provide a written justification.

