8.2.3 Relationship to Study Medication/Study Device/Procedure

The Investigator must assess the relationship of each reported AE. The Investigator must make an assessment of the relationship of the AE to the study medication/study device/procedure using the following scale:

- Unrelated: The AE is definitely not or unlikely to be associated with study medication/study device/procedure and is judged due to causes other than the study medication/study device/procedure.
- Related: The AE is possibly or probably related with study medication/study device/procedure.

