8.2.5 Laboratory Test and other Test Abnormalities as Adverse Events

A laboratory or other test (ECG, vital signs) abnormality should be reported as an AE if the Investigator considers the abnormality an AE or if the abnormality is associated with accompanying symptoms, requires medical/surgical intervention, leads to a change in study treatment, or results in discontinuation from the trial. When possible, syndromes not laboratory values, should be reported as AEs. For example, elevated hepatic transaminases associated with hepatitis should be reported as “hepatitis” and decreased hemoglobin and hematocrit requiring iron supplementation should be recorded as “anemia.”

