8.2.6 Serious Adverse Events

The Investigator is required to determine if each AE is a Serious Adverse Event (SAE). An SAE is any AE occurring after the first dose of study medication and results in any of the following outcomes:

- Death, or
- Is life-threatening, or
- Prolongation of existing hospitalization, or
- Results in a persistent or significant incapacity or substantial disruption of the ability to conduct normal life functions, or
- Is a congenital anomaly/birth defect.

Important medical events that may not result in death, be life threatening, or require hospitalization may be considered SAEs when, based upon appropriate medical judgment, they may jeopardize the patient and may require medical or surgical intervention to prevent one of the outcomes listed in this definition.

In the event of death, the cause of death should be recorded as the SAE (death is an outcome, not the AE itself).

Any planned procedures that require admission to hospital as well as any planned elective procedures (e.g., angioplasty) are not considered SAEs (unless the underlying condition has worsened or the procedure results in a worsening of the patient’s condition). In addition, pregnancy that occurs during the course of the study or absence of a treatment effect will also not be considered to be an SAE and will be collected on a separate CRF.

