8.2.7 Reporting for SAEs (24 Hours)

Regardless of causality, an SAE must be followed clinically until resolution or stabilization.

All SAEs after the first dose of study medication must be reported to the Sponsor or the Sponsor’s representative within 24 hours of the investigational site’s knowledge of the

occurrence. The investigational site will either telephone the report to the Sponsor's Medical Monitor (contact information found on the Protocol Title Page) or transmit by email a Serious Adverse Event Report (SAER) to the Sponsor's Medical Monitor or the Sponsor's representative. If the initial report is made via telephone, a completed SAER must be emailed within 24 hours of the site's knowledge of the event. Investigational sites will be provided with SAER forms.

The SAE information phoned or emailed to the Sponsor or the Sponsor's representative will include the following (as available):

- Patient Number, Investigator name, and Site Number
- SAE information: event term, onset date, severity, and causal relationship
- Basic demographic information (e.g., age, gender, weight)
- The outcomes attributable to the event (death, a life-threatening adverse drug experience, inpatient hospitalization or prolongation of existing hospitalization, a persistent or significant disability/incapacity, other important medical event[s])
- A summary of relevant test results, pertinent laboratory data, and any other relevant medical history
- The first and last dates of study medication administration
- A statement whether study medication was discontinued or study medication administration schedule modified
- A statement whether event recurred after reintroduction of study medication if administration had been discontinued or withheld
- Supplemental anonymized information may include the following hospital records: laboratory results, radiology reports, progress notes, admission and emergency room notes, holding/observation notes, discharge summaries, autopsy reports, and death certificates

The SAER should be emailed within 24 hours with as much of the above information as available at the time. Supplemental information may be transmitted using a follow-up report and should not delay the initial report.

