12.7.1 Adverse Events

AEs will be classified into standardized medical terminology from the verbatim description (Investigator term) using the Medical Dictionary for Regulatory Activities (MedDRA). AEs will be presented by preferred term nested within System Organ Class. Verbatim description and all MedDRA level terms, including the lower level terms, for all AEs will be contained in the data listings of the CSR.

AEs will be summarized by presenting, for each treatment group, the incidence of AEs. Although a MedDRA term may be reported more than once for a patient, that patient will be counted only one time in the incidence count for that MedDRA term.

Treatment-emergent adverse events (TEAEs) will be analyzed. AEs that are not treatment-emergent will be listed. A TEAE is defined as

- AEs that emerge during treatment, having been absent at pretreatment, or
- Reemerge during treatment, having been present at pretreatment but stopped prior to treatment, or
- Worsen in severity or frequency during treatment relative to the pretreatment state, when the AE is continuous.

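### The expected-event exclusion in section 8.2.1 has no exception for seriousness, so some non-fatal serious events can miss SAE status and the 24-hour report

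*Combined protocol and SAP*

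**What the plan says.** Section 8.2.1 opens with the usual broad definition of an AE, for which no causal link is needed. It then sets aside a class of expected medical events: those that the investigator perceives as reasonably common in patients who have had cardiac surgery with cardiopulmonary bypass (CPB) and are ventilated in the ICU. Of these it says: "Such events will not be considered adverse events unless the investigator considers the event to be associated with study medication, study device, or to be" worse or more frequent than expected in that patient. The protocol gives no list of such events and no threshold.

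Other sections build on that definition:

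- Section 8.2.6: "An SAE is any AE occurring after the first dose of study medication and results in any of the following outcomes". The listed outcomes are death, threat to life, prolonged hospital stay, incapacity and congenital anomaly. Important medical events outside the list may be considered SAEs on medical judgement.
- Section 8.2.6, on deaths: "In the event of death, the cause of death should be recorded as the SAE".
- Section 8.2.7: "All SAEs after the first dose of study medication must be reported to the Sponsor" or its representative, within 24 hours of the site's knowledge.
- Section 8.2.3, on what counts as related: "The AE is possibly or probably related with study medication/study device/procedure".
- Section 12.7.1: "Treatment-emergent adverse events (TEAEs) will be analyzed. AEs that are not treatment-emergent will be listed".

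Two further sections make certain findings AEs without mentioning expected events. Under section 8.2.5 a laboratory, ECG or vital-sign abnormality is to be reported as an AE if, among other triggers, it "requires medical/surgical intervention, leads to a change in study treatment, or results in discontinuation from the trial". For the physical examination, section 8.1.2 says: "Clinically significant changes from Screening will be recorded as AEs".

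**The concern.** Whether an event is serious and whether it is expected are separate questions. A complication can be familiar after bypass surgery and still threaten life or keep the patient in hospital. Section 8.2.1 lets the answer to the second question settle the matter before the first is asked, because an event that is not an AE never reaches the seriousness decision.

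Safety and tolerability is a secondary objective (section 3.2). Section 2.2.2 says there have been no clinical trials of VentaProst so far. The study is open-label (section 6.5) and has no concurrent control group to show the background rate of post-CPB events, so the judgement that an event is merely expected rests on each investigator's perception. An event excluded at that point would reach neither the sponsor within 24 hours nor the AE summaries and listings.

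**Working it through.** The plan states no figure on this point and no arithmetic applies. The check follows the definitions from one section to the next.

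1. *Entry to AE status (8.2.1).* An event of the expected type is an AE only if it is considered associated with study medication or device, or is beyond expectation in severity or frequency. Meeting a seriousness criterion is not a route back.
2. *Entry to SAE status (8.2.6).* An SAE must first be an AE, and the investigator is asked to decide on seriousness for each AE, not for each event.
3. *Entry to the 24-hour report (8.2.7).* The trigger is an SAE.

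For an event of the expected type after the first dose of study medication, this gives:

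| Event | AE under 8.2.1 | SAE under 8.2.6 | 24-hour report |
|---|---|---|---|
| Serious; considered associated with drug or device | Yes | Yes | Yes |
| Serious; unrelated, but unexpectedly severe or frequent | Yes | Yes | Yes |
| Fatal; unrelated and of the usual kind | Not by 8.2.1 | Cause of death recorded as SAE by its own sentence | Yes |
| Non-fatal, but life-threatening, prolonging hospital stay or incapacitating; unrelated, usual severity and frequency | No | No, unless judgement is used | Not required |
| Non-serious; unrelated, usual severity and frequency | No | No | No, as intended |

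The fourth row is the gap. Congenital anomaly is left out of it because it is not a realistic everyday event of post-CPB care.

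I then looked for wording elsewhere that would close the gap:

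- The phrase on causality that opens 8.2.7 governs the follow-up of an SAE. It does not turn an excluded event into one.
- The rules in 8.2.4 on sequelae and fatal outcomes start from an AE.
- The important-medical-event clause in 8.2.6 is permissive.
- Severity is graded in 8.2.2 on a different scale from seriousness in 8.2.6, so the exception for unexpected severity does not stand in for seriousness.
- The relatedness scale in 8.2.3 is applied to reported AEs, after 8.2.1 has decided whether there is one. It is reasonable to read association in 8.2.1 by the same scale, and that narrows the gap without closing it.
- The last paragraph of 8.2.7, on serious and unexpected events, sets the minimum content for regulatory reports. It does not enlarge the SAE definition.

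For the output, 12.7.1 covers AEs that are treatment-emergent (analysed) and AEs that are not (listed). An event that was never an AE falls under neither.

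**The case against.** The exclusion is a deliberate and sensible rule for patients in whom untoward events are routine, and much gets past it. Association with drug or device, unexpected severity and unexpected frequency each restore AE status, and a possible relation is enough. What remains must be routine, serious, not even possibly related, and no worse or more frequent than usual. Hemodynamics, concomitant medications, end-of-study laboratory tests and reasons for discontinuation are collected in any case. All of this stands, and it makes the gap narrow. It does not close it: these data neither identify an SAE nor start the 24-hour clock.

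Three stronger readings are tempting, and the documents do not support them.

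- A reader might infer that the drug's own named risks would be lost. Section 2.2.5 lists bleeding and systemic vasodilation as theoretical effects, and a site could call such events expected after CPB. But naming them as mechanism-based risks makes a possible relation easy to assign. Section 5.4.1 also makes severe mediastinal bleeding and hemoptysis pre-defined grounds for conversion, which makes it harder to pass them off as unremarkable.
- A reader might infer that 8.2.5 and 8.1.2 flatly contradict 8.2.1 and should override it. They overlap: a blood pressure fall regarded as routine but treated is an AE under 8.2.5 and may not be one under 8.2.1. The sections can be read as specific rules in their own field, although the text does not say so. Overriding 8.2.1 for every such finding would go too far. Screening is pre-operative, so ordinary consequences of surgery would become AEs and the rule would be largely undone.
- A reader might infer that the references to unanticipated events in footnote 4 of Tables 1 and 2 and in sections 10.1.2, 10.1.3 and 10.2.2 widen the gap. The footnote is inclusive and excludes nothing. Those sections come before the VentaProst treatment sections, which simply ask for AEs to be recorded.

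**Conclusion.** The point holds in a limited form. As written, the plan lets a non-fatal event of the expected type that meets the life-threatening, prolonged-hospitalization or incapacity criterion go without SAE status, without the 24-hour report and without an entry in the AE summaries or listings. This happens when the investigator judges it unrelated and of usual severity and frequency.

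It does not extend to deaths, for which 8.2.6 has a separate sentence, or to all serious events. How often it would occur cannot be estimated, since the documents give no event rates. A reader might infer a size from the enrolment, as one patient is a large share of about 10 per part. That is only the reciprocal of the sample size. It says nothing about how often the exclusion would bite, and section 12.7 does not define a separate SAE incidence summary to which it would apply.

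The conclusion rests on reading the SAE definition as written, as a subset of AEs, and on the investigator not using the discretionary important-event clause. The change is recommended because it closes a reporting gap in a first trial of the product at little cost.

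**What to change.** Add one sentence to section 8.2.1: the expected-event exclusion does not apply to any event after the first dose of study medication that meets a seriousness criterion in 8.2.6; such an event is recorded as an SAE and reported under 8.2.7 whatever its expectedness or attribution. Keep the exclusion for non-serious events.

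The cost is a few more SAE entries and reports in about 20 patients (about 10 in each of two parts). No new assessment or analysis is needed.

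Optionally, state how 8.2.1 is to be read alongside 8.2.5 and 8.1.2, so that sites handle the overlap alike. This need not make every such abnormality an AE.
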